Outcome measures. The primary measure of this study will be the breakpoint, which is the schedule (number of button presses) at which the individual stops to work for more alcohol. Also, the BrAC exposure measures will be determined. Alcohol craving in response to ghrelin will be measured using the Alcohol Visual Analogue Scale (A-VAS) and the Alcohol Urge Questionnaire (AUQ) during the PR sessions. Sensitivity to alcohol will be measured using the Drug Effects Questionnaire (DEQ), Biphasic Alcohol Effects Scale (BAES), and the Profile of Mood States (POMS), repeatedly during the PR sessions and the CASE Experience Questionnaire (CEQ) at the end of all sessions. fMRI BOLD signal in brain areas associated with incentive salience and areas associated with reward circuitry (including the ventral striatum) will be measured during the “fMRI/alcohol clamp” session. This study may facilitate the identification of a novel neuropharmacological target, thus facilitating the development of novel pharmacological treatments for alcoholism.

• Table of Contents

Precis	3
Introduction	6
Study objectives	21
Subjects	22
Study Design and Methods	23
Storage of data and samples	32
Additional Considerations	32
Risks and discomforts	32
Subject safety monitoring	36
Outcomes measures	37
Statistical Analysis	37
Human Subjects Protection	38
Anticipated Benefit	40
Classification of risk	40
Consent documents and process	40
Data and Safety monitoring	41
Quality Assurance	41
Alternatives to participation or Alternative therapies	41
Confidentiality	41
Conflict of Interest	42
Technology Transfer	42
Compensation	42
References	42

• List of Abbreviations

AE	Adverse Events
AD	Alcohol Dependence
AEFQ	Alcohol Effects Questionnaire
A-VAS	Alcohol Visual Analogue Scale
ARC	Arcuate Nucleus
AUDIT	Alcohol Use Disorders Identification Test
AUQ	Alcohol Urge Questionnaire
BAES	Biphasic Alcohol Effects Scale
BAS	Behavioral Approach System
BIS	Behavioral Inhibition System
BMI	Body Mass Index
BP	Blood Pressure
BASDA	Brief Addictive Behavior Social Density Assessment
BOLD	Blood Oxygen Level Dependent
BAC	Blood Alcohol Content
BrAC	Breath Alcohol Concentration
BrCO	breath carbon monoxide
CASE	Computer-Assisted Self-infusion of Ethanol
CBC	Complete Blood Count
CEQ	CASE Experience Questionnaire
CIWA	Clinical Institute Withdrawal Assessment
CeA	central nucleus of the amygdala
CPP	Conditioned Place Preference
CPRS	Comprehensive Psychopathology Rating Scale
CR	Cue-Reactivity
CRF	Corticotropin-Releasing Factor

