
[figure not shown]
Figure 3.

Legend: between-sessions correlations for number of button presses (3A), total rewards earned (3B), peak BrAC (3C), and average BrAC (3D).

Furthermore, total ethanol self-administered during the PR schedule was significantly associated with drinking days measured with the TimeLine Follow-Back (TLFB) (Figure 4), thus indicating the clinical relevance of this procedure given its ability to reproduce in the human lab setting, the alcohol use in the naturalistic milieu.

[figure not shown]
Figure 4

Legend: significant association between total ethanol self-administered during the PR schedule and drinking days.

Additionally, in this study we also found that total ethanol self-administered during the whole PR schedule was significantly associated with the Drug Effects Questionnaire (DEQ) score (considering its peak value) for measures of “wanting” (Fig. 5A), as well as with the DEQ score for “wanting” following the priming (Fig. 5B).

Figure 5

Legend: significant association between total ethanol self-administered and both DEQ “Want” score during the whole PR procedure (A) and following the priming (B).

Additional interesting results of this study were that total ethanol self-administered during the PR schedule was significantly associated with DEQ scores for measures of “feeling” and “liking” drug effects, as well as “high” and “intoxication” were positively associated with number of button presses. Alcohol Urge Questionnaire (AUQ) maximum measures were significantly associated with total ethanol and number of button presses. Biphasic Alcohol Effects Scale sedation measure after priming was strongly associated with peak BrAc, average BrAC, and total rewards earned.

In summary, these results demonstrate that the PR IV alcohol infusion procedure has good test-retest reliability and demonstrate that this method is sensitive to the rewarding and motivational properties of alcohol.

fMRI/alcohol clamp

The goal of the second paradigm is to investigate possible mechanisms of action of ghrelin through the use of two slightly different but related fMRI procedures. Specifically:

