The primary objective of this protocol is to investigate whether ghrelin alters alcohol's pharmacologic effects, including motivation for alcohol reward, as well as subjective measures of craving, and the subjective responses to alcohol in heavy drinkers receiving IV administrations of ghrelin and alcohol.

a. Primary objectives

The primary measure of this study will be the breakpoint, which is the schedule (number of button presses) at which the individual stops to work for more alcohol.

b. Secondary objectives

Secondarily, the BrAC exposure measures will also be determined, that is the highest (max) BrAC, average BrAC and the area under the BrAC-time curve determined for each subject. Urge to drink and alcohol sensitivity will be measured during the PR session. Adverse events will also be assessed in order to assess the safety of the IV co-administration of ghrelin and alcohol. Also, during the "fMRI/alcohol clamp" session, fMRI will be used to see whether ghrelin affects the activation of the ventral striatum (VS) in anticipation to work for alcohol reward and the incentive salience of cues in subjects who will subsequently receive IV alcohol administration. In

addition to the VS, other fMRI ROI's are the amygdala, insula and OFC. Adverse events will also be assessed during the fMRI/alcohol clamp sessions.

Furthermore, an additional secondary aim will be an exploratory analysis of the role of genetic polymorphisms of both ghrelin and ghrelin receptor genes – detailed in page 14 – as possible moderators of ghrelin's effects on the primary aim ('breakpoint', i.e. number of button presses in the IV alcohol PR procedure).

3. Subjects:

a. Description of study populations

Male and female adults will be eligible to participate in this study. Participants will be non-treatment seeking heavy drinking volunteers. Our goal is to screen 124 subjects and recruit 62 individuals. Assuming a 20% drop-out rate, we will reach 50 completers.

b. Inclusion criteria

1. Male and female participants between 21-60 years of age.
2. Good health as determined by medical history, physical exam, ECG and lab tests.
3. Creatinine \leq 2 mg/dl.

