The PR schedule self-administration will be conducted using the Computer-Assisted Self-infusion of Ethanol (CASE) system (currently being used in two NIH protocols 08-AA-0137 and 08-AA-0178). Just prior to the start of the PR schedule session, the subject will be reminded of the procedure for obtaining alcohol during the session. Following a 15-min priming interval (that will not be applied here, as our ‘priming’ is the IV bolus of ghrelin), the PR period lasting 120 minutes begins. Each standardized exposure will follow a slopelet pattern (linear increase of 7.5 mg% over 2.5 min followed by a linear decrease of 0.5 mg%/min until the next exposure). The PR schedule will escalate geometrically from using a progressive ratio that will be empirically established. An initial PR schedule will be established based on simulations using the model published by Richardson and Roberts.¹⁴⁷ For practical considerations, we will select a schedule that requires 2 button presses for the first exposure and escalates exponentially to requiring ~15,000 button presses for the 20th exposure. This initial schedule will be tested in the first 6 subjects, and the range of break-points obtained will be evaluated. If there is insufficient variability in the break-points across the first 6 subjects, the schedule may be adjusted before proceeding with the enrollment of other subjects. Within 0.5 seconds of pushing the drink button, the CASE system software will begin infusing the alcohol necessary to produce the desired increase in BrAC exposure from the BrAC level at the time the button was pushed. Also, if the CASE system predicts that an additional drink selected by the participant would result in a peak BrAC 0.12 (which is the upper limit for BrACs achieved in this study), then the push button will be inactivated, with the subject’s knowledge, until the time when the predicted peak BrAC is below the upper limit.

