NCI Common Terminology Criteria for Adverse Events v. 3.0 will be used for grading and reporting adverse events.¹⁶⁷

Criteria for individual subject withdrawal

- A Serious Adverse Event (SAE) that is judged by the Investigators as being related to the study drug;
- Pregnancy;
- At the discretion of the Principal Investigator (PI) based on adverse event (AE) severity;
- Non-compliance with protocol procedures or investigator request(s);
- Patient request.

Enrolled subjects who show up with positive UDT or BrAC $\geq 0.08\%$ at one of the four experimental sessions (excluding the night before visits 2-5) will not perform the session. In this case, the experimental session may be re-scheduled at the PI discretion. Additionally, a session may be rescheduled for other medical reasons for which the PI and/or MAI think it is in the best interest of the participant to re-schedule the session. However, if the subject will repeatedly show up with positive UDT or BrAC $\geq 0.08\%$ at repeated visits, the PI may withdraw him/her from the study.

9. Outcome measures

a. Primary outcome measures

The primary measure of this study will be the breakpoint, which is the schedule (number of button presses) at which the individual stops to work for more alcohol during the PR sessions.

b. Secondary outcome measures

Alcohol exposure will be measured via BrAC exposure measures, i.e. highest BrAC, average BrAC and the area under the BrAC-time curve and by BAC when subjects are in the fMRI scanner. Alcohol craving will be measured using the Alcohol Visual Analogue Scale (A-VAS) and the Alcohol Urge Questionnaire (AUQ). Sensitivity to alcohol will be measured using the Drug Effects Questionnaire (DEQ), Biphasic Alcohol Effects Scale (BAES), and the Profile of Mood States (POMS), repeatedly during the PR session and the CASE Experience Questionnaire (CEQ)

at the end of all sessions. fMRI BOLD signal in brain areas associated with incentive salience and areas associated with reward circuitry (including the ventral striatum) will be measured during the “fMRI/alcohol clamp” session.

10. Statistical Analysis

1. Analysis of data/ study outcomes

Analysis of data/study outcomes

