Outcome data will be examined for homogeneity of variance, and if necessary transformed to meet this criterion. Most of the analyses will consist of repeated measures ANCOVAs to accommodate dependent measures assessed at multiple time points. When the dependent measure is just assessed once then a regular ANCOVA will be used. We will examine medication main effects across several different dependent measures.

Criteria for significance

A probability level of 0.05 or lower will be considered significant.

2. Power analysis

Power analysis

A generic calculation of power for a two-means comparison to detect an effect size of Cohen's $f \geq 0.4$ (large effect size) with a sample size of 50 yields a power estimate ≥ 0.80 at alpha=0.05. The relative effect size chosen (“large” effect size) for the power calculation is based on the observation that laboratory studies typically yield larger effect sizes than clinical trials, including, for example, our recent (unpublished; PI: [name]) human lab studies using the

IV Alcohol PR procedure, described above and representing the study our primary aim (number of button presses) is based upon.

Furthermore, the sample proposed here provides sufficient power (power estimate ≥ 0.80 at alpha=0.05) to detect ghrelin's effects on fMRI BOLD activation in the VS, consistent with the unpublished data (PI: [name]; data already mentioned above) with varenicline (n = 8) vs. placebo (n = 7) indicating significantly higher BOLD activation in the varenicline group.

Accrual number request, taking into account screening/ dropouts

In the Brown University study with IV ghrelin, inclusionary/exclusionary criteria were similar and about 50% of the subjects screened were eligible and randomized. Consistent with other human laboratory studies with a similar study length, we also expect that a number up to 20% will not complete the study. Therefore, we anticipate a number-needed-to-screen of 124 subjects, with 62 being randomized and 50 completers.

11. Human Subjects Protection

a. Subject selection

Adults who fulfill the qualification criteria will be included, regardless of race, ethnicity, sex, or religious affiliation.

b. Justification for inclusion of children

Children will not be included because the study proposed involves the administration of alcohol. It is illegal to give alcohol to individuals below 21 years of age.

c. Justification for inclusion or exclusion of other vulnerable subjects

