Vulnerable participants will not be enrolled. Females who show a positive urine pregnancy test will be withdrawn from the study. Women of child-bearing potential (i.e. who are pregnant or who are trying to become pregnant) will not be included, because it is inappropriate and unethical to give alcohol to women who are pregnant because of the risk of fetal alcohol syndrome. Females of childbearing potential who are sexually active and have not been surgically sterilized must agree to use a reliable method of birth control during the study (**details above in section 3b, Inclusion criteria, #4**). Furthermore, a urine pregnancy test will be performed at each session.

d. Justification of sensitive procedures

This study employs the use of placebo to evaluate the effects of ghrelin. This is the required standard set by the FDA for evaluation of drugs. The previous outpatient human laboratory study conducted at Brown University was a placebo-controlled study and FDA reviewed its protocol.

The hypothesis of this protocol is that IV ghrelin will temporarily increase the likelihood that participants will self-administer alcohol during the PR session and will increase craving. The possible temporary increase in alcohol administration and craving is a necessary challenge to evaluate the ghrelin system as a novel neuropharmacological target for alcoholism. It should be noted that at this stage ghrelin administration cannot be considered a standard provocative test. Although very preliminary data from the Brown study suggest so, this is a very early stage research. The possibility that IV ghrelin increases temporarily alcohol administration and craving is in fact the main objective measure of this project. The study at Brown was an outpatient study

and its safety profile was excellent. This protocol will enroll outpatients who, however, will stay overnight at the NIH Clinical Center before and after each session (two nights per session).

e. Safeguards for vulnerable populations

Vulnerable populations will not be studied. Urine pregnancy tests will ensure that alcohol is not administered to women who may be pregnant.

f. Qualifications of investigators

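### DEQ, BAES and POMS are rated in sessions where participants set their own alcohol exposure, so the planned ghrelin main effect is a total effect, not changed sensitivity to a given alcohol level

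*Combined protocol and SAP*

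**What the plan says.** All references are to the combined protocol and SAP.

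- **Objective.** The Precis lists as a secondary aim whether ghrelin alters urges and the subjective response to IV alcohol. Section 2 frames the overall objective as a change in alcohol's pharmacologic effects.
- **Where response is rated.** Section 2b: "Urge to drink and alcohol sensitivity will be measured during the PR session". Section 9b ties the sensitivity scales to that session: DEQ, BAES "and the Profile of Mood States (POMS), repeatedly during the PR session and the CASE Experience Questionnaire (CEQ". Only the CEQ is given after every session.
- **Where craving is rated.** The Precis says "Alcohol craving in response to ghrelin will be measured using the Alcohol Visual Analogue Scale (A-VAS" and goes on to place A-VAS and AUQ in the PR sessions. Section 9b names the same two scales but no session. Section 8 puts them in the battery for every study visit and leaves the times to a flow sheet. Section 4d lists an urge rating in the PR visits before the catheters go in.
- **Alcohol in the PR session.** Section 4d: each earned reward is a "linear increase of 7.5 mg% over 2.5 min followed by a linear decrease of 0.5 mg%/min until the next exposure", with a ceiling at BrAC 0.12. The 15-minute priming interval is not used in this trial.
- **Expected direction.** Section 11d: "IV ghrelin will temporarily increase the likelihood that participants will self-administer alcohol during the PR session and will increase craving".
- **The team's own PR study.** The Introduction (PR IV Alcohol Procedure) links DEQ scores to total ethanol taken and adds "Alcohol Urge Questionnaire (AUQ) maximum measures were significantly associated with total ethanol and number of button presses".
- **Analysis.** Section 10 plans repeated measures ANCOVA: "We will examine medication main effects across several different dependent measures". It names no covariate, and BrAC appears only as a separate outcome in sections 2b and 9b.

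**The concern.** Sensitivity means the response to a given amount of alcohol. In the PR sessions the amount is not given: each person sets it by pressing, and the primary hypothesis is that ghrelin raises it. If that hypothesis is right, DEQ, BAES and POMS can differ between the ghrelin and placebo sessions even though a given BrAC feels the same under both.

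A report that followed section 10 could then present altered subjective response as a second, independent finding when it is the extra alcohol showing up again. The error can also run the other way. If ghrelin makes each infusion feel stronger and people stop pressing sooner, a true change in sensitivity could be hidden. What is at stake is the reading of one named secondary objective.

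**Working it through.** **1. The plan's own figure.** Section 10 claims power of at least 0.80 for Cohen's f of 0.4 with 50 participants. For two groups, f = 0.4 is d = 0.8. With 25 per group the noncentrality is 0.8 × √(25/2) = 2.83, and power is 0.79 (noncentral t) or 0.81 (normal approximation). A paired test with n = 50 and a standardised difference of 0.4 has the same noncentrality, 0.4 × √50 = 2.83, and power 0.79. The figure reproduces and is not disputed. It also makes 0.4 SD a convenient illustrative shift, because 50 pairs would usually detect it.

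**2. How far exposure can diverge.** The initial schedule in section 4d runs from 2 presses to about 15,000 at the 20th exposure. The step ratio is (15,000/2)^(1/19) ≈ 1.6. The first five exposures therefore cost 2 × (1.6⁵ − 1)/(1.6 − 1) ≈ 32 presses in all. Assuming back-to-back requests, they give 5 × 7.5 = 37.5 mg% in 5 × 2.5 = 12.5 minutes, before the first 15-minute BrAC reading. Someone who does not press stays at zero. With no priming dose, the text describes no common alcohol exposure in the session.

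**3. Size of the carry-over.** The documents give neither the ghrelin effect on BrAC nor the correlation between BrAC and score differences. Both are assumed:

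- n = 50 paired differences, two-sided 0.05 (section 10 does not state sidedness).
- BrAC difference X with mean D and SD 1.
- Score difference Y = rX + √(1 − r²)·e, with no direct ghrelin effect.

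Then Y has mean rD and SD 1, and the paired test has noncentrality rD√50. For D = 0.4:

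- r = 0.3: 0.12 × 7.07 = 0.85, power 13%
- r = 0.5: 0.20 × 7.07 = 1.41, power 28%
- r = 0.7: 0.28 × 7.07 = 1.98, power 49%

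Simulation (20,000 runs per setting) agrees and shows the range:

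| BrAC shift D | r = 0.3 | r = 0.5 | r = 0.7 |
|---|---|---|---|
| 0.2 | 7% | 11% | 16% |
| 0.4 | 13% | 28% | 49% |
| 0.6 | 24% | 55% | 83% |

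**4. What BrAC adjustment buys.** In the same simulation, regressing the score difference on the BrAC difference and testing the intercept brings rejection back to about 5%. That holds only if nothing unmeasured drives both intake and rating. With one assumed shared driver (loading 0.5 on dose, 0.4 on score), rejection after adjustment is about 6%, 10% and 15% for D = 0.2, 0.4 and 0.6, and 20% at D = 0.8. Adjustment helps, but it does not restore a randomised comparison.

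**The case against.** The best reply is that nothing here is biased. Randomised order protects the total effect of ghrelin on every score, and BrAC is read every 15 minutes. ANCOVA is the named method with its covariates left open, so the data for a BrAC-aware analysis will exist. The flow sheets, which hold the rating times, were not available and may already schedule a rating after the bolus and before alcohol, or ratings during the clamp. The team's PR associations come from 28 social drinkers and appear to be across people, so they do not establish the within-person correlation used above.

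Most of this stands, and it rules out several stronger readings that a reader might infer:

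- *The two effects can never be separated.* Not supported. What is missing is a pre-specified analysis, not the data.
- *13% to 49% is a false-positive rate to set against 5%.* Not supported. It is the power to detect a real indirect effect, which misleads only if reported as sensitivity at a given BrAC.
- *Craving is compromised in the same way.* Not supported. Craving is also in the per-visit battery and is collected before catheter placement. Urge may drive pressing rather than follow it: the same PR study linked DEQ wanting after priming to total intake.
- *The adverse-event comparison is invalid.* Not supported. The safety of giving ghrelin with alcohol properly includes any extra alcohol taken, and adverse events are also assessed in the clamp sessions.

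What the reply does not answer is that no text supplied commits DEQ, BAES or POMS to a comparison at matched alcohol exposure.

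**Conclusion.** The point holds for DEQ, BAES and POMS under the planned analysis. The medication main effect estimates ghrelin plus any change in alcohol taken, whereas the objective concerns response to alcohol itself. If ghrelin shifts BrAC by 0.4 SD and acts on a score only through BrAC, the unadjusted test would be significant in 13% to 49% of trials of 50 completers (r from 0.3 to 0.7), and the result would be misattributed to sensitivity. The shift and the correlation are assumptions; the identification problem does not depend on their values.

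The breakpoint analysis is not touched. Confidence is moderate, because rating times sit in flow sheets that were not available. The change is worth making because it alters what can be concluded on a stated secondary objective.

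**What to change.** 1. **Section 10, labelling.** State that the unadjusted ghrelin-placebo contrast on DEQ, BAES and POMS is a total effect that includes any difference in alcohol taken, and will not be reported as changed sensitivity.
2. **Section 10, supportive analysis.** Pre-specify a repeated-measures model for these scales with the time-matched 15-minute BrAC reading as a time-varying covariate. State its limit alongside: BrAC is post-randomisation, so the adjusted estimate is unbiased only if no unmeasured factor drives both intake and rating.
3. **Sections 2b and 9b, craving.** For craving in response to ghrelin, name the A-VAS/AUQ rating after the 10-minute bolus and before alcohol is available as the key time point. Use it if the flow sheets already schedule it; otherwise add one short rating.
4. **Optional.** DEQ, BAES and POMS at matched BrAC in the clamp sessions would be a cleaner test. It is usable only after the two descriptions of clamp alcohol are reconciled: the Precis calls it a fixed dose, while the Precis and section 4d also make the amount depend on points earned.

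The cost is a few sentences in sections 2b, 9b and 10 and at most one brief extra rating, plus short clamp ratings if the optional step is taken. Sample size and the breakpoint analysis stay as they are.
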